Previous studies have consistently shown that DENV-4 infections are relatively rare compared to other serotypes. A study in Vietnam found a low number of DENV-4 cases, illustrating the lower incidence of DENV-4 than other serotypes (Ta et al., 2019). A similar study in the Philippines, assessing the efficacy of a tetravalent dengue vaccine candidate (TAK-003) for DENV-4 in eight dengue endemic countries in Asia and Latin America was difficult due to the small number of DENV-4 infection cases, only 7 cases were virologically confirmed (Biswal et al., 2019).

A study on the prevalence and clinical aspects of DENV-1, DENV-2, DENV-3, and DENV-4 in Indonesia showed that DENV-4 was the least common circulating serotype (Harapan et al., 2019). A study conducted in many hospitals examining acute febrile illness in hospitalized patients (AFIRE), found that DENV-4 infection was less common among the cases studied (Utama et al., 2019). Interestingly, DENV-4 is often found in outpatients or during dengue outbreaks. A study in outpatients in West Java found that DENV-4 infection occurred as frequently as other serotypes, but most cases were not clinically typical (Kosasih et al., 2016). In the 2004 Jakarta outbreak, DENV-4 was the second most common serotype after DENV-3 (Suwandono et al., 2006). A study conducted during a dengue outbreak in Jember in 2019, has identified genetic factors associated with DENV-4, suggesting that a combination of selection pressure and changes in genetic mutations may contribute to the dominance of DENV-4 in East Java, Indonesia (Wardhani et al., 2023; Aryati et al., 2020).

One possible explanation for the low prevalence of DENV-4 is that most studies are hospital-based, which may not include untreated mild DENV-4 infections. Besides, NS-1 screening, which is used for detection and identification of DENV-4 cases, has low sensitivity, which further complicates accurate diagnosis (Mata et al., 2020; da Costa et al., 2014). In addition, the sensitivity of NS1 detection varies among secondary infections, with the highest sensitivity of DENV-3 (47.1%), followed by DENV-1 (40.9%), DENV-2 (30%), and DENV-4 (27%) (Kosasih et al., 2013). This is important as secondary

infections of DENV-2, DENV-3, and DENV-4 in Southeast Asia are commonly associated with severe clinical manifestations, indicating the potential for a significant health burden (Soo et al., 2016).

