2.2. Secondary objectives

- To assess the prevalence of dengue virus infection among patients with acute fever
- To assess the prevalence of infection with DENV-4 and other serotypes as well as clinical characteristics, immunologic and virologic profiles important for vaccine trials and implementation
- To assess human and viral factors associated with severity of febrile illness due to dengue virus infection
- To increase the capacity of Tangerang District Hospital's Infectious Disease Laboratory/ INA RESPOND Reference Laboratory to perform plaque reduction neutralization test (PRNT).
- To identify other etiologies of fever in Tagerang district

III. CLINICAL HYPOTESIS

Dengue fever is a hyperendemic disease in Tangerang district, Indonesia.

DENV-4 infection is more frequently found at the primary health centers than at the hospital because the clinical symptoms are milder.

Several human and viral factors, such as age, nutrition status, immune status, serotypes, types of infections (primary/secondary) are associated with severity of symptoms.

IV. ETHICAL APPROVAL

This study will be conducted in accordance with ethical guidelines and obtained permission from the relevant institutions and the ethics committee of Tangerang District Hospital.

V. METHOD

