5.2. Inclusion and exclusion criteria

Inclusion criteria:

1. Patients age \geq 4 years old with fever ($\geq 37.5^{\circ}\text{C}$) or history of fever with antipyretic use, lasting less than or equal to 7 days
2. Presence at least one of the following dengue-like symptoms:
 - Headache
 - Retro-orbital pain
 - Nausea/ vomiting
 - Muscle, bone, or joint pain
 - Rash or bleeding manifestations
3. Patient or patient's guardian giving consent to participate in the study

Exclusion criteria:

1. Have a condition that may interfere with study procedures and compliance (based on doctor's assessment)
2. Suspected of focal infection

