5.5. Clinical data and specimen collection time

- Hospitalized participants**

The data and specimens to be collected are data at the time of the first visit to the hospital and at the second visit. For participants with a positive NS1 RDT result at the first visit, second visit data will be collected when the participant is scheduled to be discharged from hospital inpatient care. For participants with a negative NS1 RDT result at the first visit, data for the second visit will be collected within 7-14 days of the first visit.

- **Participants from Public Health Centers**

Data and specimens to be collected are data and specimens at the time of the visit to the public health centers, while the second data and specimens are only taken as much as 25% of the number of participants of the first visit, with a window period of 7-14 days after the first visit. The determination of participants for the second visit is determined by study's team based on clinical judgment.

- **Clinical evaluation**

Participants will undergo a clinical assessment to evaluate the severity of the disease, including the presence of signs of severe clinical manifestations.

- **Type and amount of specimens to be taken**

- **Serum**

Serum obtained with a 4 mL yellow cap gel separator tube, all serum specimens obtained will be sent to Tangerang District Hospital's Infectious Disease Laboratory/INA-RESPOND lab for viral culture and PRNT.

- **Whole blood dan plasma**

Whole blood specimens in 3 mL purple cap EDTA tubes (adult) or 2 mL purple cap EDTA tubes (pediatric) will be used for hematology test, RDT IgM/IgG, and RDT-NS1 testing, the remaining plasma will be sent to Tangerang District Hospital's Infectious Disease Laboratory for ELISA and PCR testing.

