5.6. Laboratory test

- **Hematology**

Hematology test is conducted at PHCs and Tangerang District Hospital using an automatic hematology analyzer, and the results will be given to the doctor in charge as a basis for diagnosis and therapy.

- **Antigen**

NS1 antigen will be tested at PHCs and Tangerang District Hospital using RDT, and the results will be provided to the doctor in charge as a basis for diagnosis and therapy. The results will be confirmed by NS1 antigen by ELISA.

- **Molecular**

Blood from participants will be subjected to molecular testing. Polymerase Chain Reaction (PCR) to detect and confirm the presence of DENV, and identify dengue serotypes.

- **Serology**

Enzyme-Linked Immunosorbent Assay (ELISA) will be used to detect dengue specific antibodies (IgM and IgG), Rapid Diagnostic Test (RDT) to detect IgM for acute dengue infection, and IgG to determine primary or secondary infection.

- **Plaque Reduction Neutralization Test (PRNT)**

PRNT will also be performed to assess serotype-specific neutralizing antibodies in a subset of specimens (specimens from all severe cases and randomized mild cases as controls).

VI. STATISTICAL ANALYSIS AND SAMPLE SIZE JUSTIFICATION

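### The severe-versus-mild PRNT contrast may be confounded by primary/secondary infection and by day of illness, and neither the control draw nor the analysis allows for either.

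*Combined protocol and SAP*

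**What the plan says.** Section 5.6 gives PRNT a purpose and a sampling rule: "PRNT will also be performed to assess serotype-specific neutralizing antibodies in a subset of specimens (specimens from all severe cases and randomized mild cases as" the comparison group). It gives no number of controls, no ratio, no matching or stratification, and no visit. The same section says that IgG will separate primary from secondary infection, but does not link that result to the PRNT draw.

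Section 5.5 sends the study serum to the "INA-RESPOND lab for viral culture and PRNT". All of this serum is drawn after fever has begun:

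- **First visit:** fever "lasting less than or equal to 7 days" (section 5.2).
- **Hospital, NS1 RDT positive:** second sample at discharge, on no fixed day.
- **Hospital, NS1 RDT negative:** "For participants with a negative NS1 RDT result at the first visit, data for the second visit will be collected within 7-14 days of the" initial one.
- **Health centers:** second sample 7-14 days later, in only 25% of participants, chosen by clinical judgment.

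The background says that secondary "infections of DENV-2, DENV-3, and DENV-4 in Southeast Asia are commonly associated with severe clinical manifestations". Section III lists infection type among the factors expected to relate to severity, and states as a hypothesis: "Dengue fever is a hyperendemic disease in Tangerang district, Indonesia".

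Section 6.2 names descriptive statistics, prevalence with confidence intervals, and comparisons of DENV-4 with other serotypes. It contains no PRNT analysis, no severe-versus-mild model and no adjustment for infection type.

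**The concern.** A factor confounds a comparison of titres if it is related both to severity and to titre. The plan supplies the first link for infection type. The second link is an assumption, because the documents do not discuss it: in a secondary infection the early antibody response is boosted and neutralizes several serotypes. If that holds, the severe group contains more high, broad titres simply because it contains more secondary infections.

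Day of illness could act in the same way. Serum may come from the first week of fever, from discharge, or from up to about day 21 (7 + 14), depending on site and NS1 result. The plan does not say which sample goes to PRNT, so severe and mild cases may be tested at different points of a changing antibody response.

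Immune responses are in the primary objective, and section III names immune status as a possible severity factor. A crude titre difference could be reported as an immune correlate of severity when it reflects infection type or sampling day. In a secondary infection, a titre against a non-infecting serotype, DENV-4 included, could be read as immunity specific to that serotype. The secondary objectives intend these profiles to inform vaccine trials.

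**Working it through.** **No figure to reproduce.** The plan gives no size, power, titre difference or SD for the PRNT subset. The site targets in section 6.3 add to 100 + 100 + 200 = 400 dengue cases, with no number for severe cases.

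**Model.** Suppose log10 titre has no relation to severity within primary or within secondary infection. Let p_S and p_M be the secondary shares in severe and mild cases, b the log10 titre gap between secondary and primary infection, s the within-type SD, and n the number per group.

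- Crude difference: d = b × (p_S − p_M). Geometric mean ratio: 10^d.
- SE = √{[s² + b² p_S(1 − p_S)]/n + [s² + b² p_M(1 − p_M)]/n}.
- False-positive rate at two-sided 5% ≈ Φ(d/SE − 1.96) + Φ(−d/SE − 1.96).

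All five inputs are assumptions.

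**First set: n = 40, s = 0.6.** Cells show the ratio, then the false-positive rate of an unadjusted Welch t-test (4,000 simulations each).

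| p_S / p_M | b = 0.5 | b = 1.0 | b = 1.5 |
|---|---|---|---|
| 70% / 60% | 1.12; 6.0% | 1.26; 8.4% | 1.41; 10.8% |
| 80% / 50% | 1.41; 18.4% | 2.00; 43.5% | 2.82; 58.0% |
| 90% / 50% | 1.58; 27.8% | 2.51; 68.8% | 3.98; 85.9% |

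Hand check of the middle cell: d = 1.0 × 0.30 = 0.30. SE = √[(0.36 + 0.16)/40 + (0.36 + 0.25)/40] = √0.02825 = 0.168. d/SE = 1.785, and Φ(1.785 − 1.96) ≈ 0.43, which agrees with the simulation.

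**Second set: n = 40, s = 0.5, with more secondary infection and smaller boosts.** Here p_S follows from p_M and the odds ratio (OR) linking secondary infection to severity. For example, at p_M = 90% and OR 2 the odds are 9 × 2 = 18, so p_S = 18/19 = 94.7%. Rates are by formula.

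| p_M | OR | b | p_S | Ratio | Rate |
|---|---|---|---|---|---|
| 50% | 4 | 1.0 | 80.0% | 2.00 | 51% |
| 70% | 4 | 1.0 | 90.3% | 1.60 | 30% |
| 70% | 2 | 1.0 | 82.4% | 1.33 | 14% |
| 90% | 2 | 1.0 | 94.7% | 1.12 | 7% |
| 50% | 4 | 0.2 | 80.0% | 1.15 | 8% |
| any | 1 | any | = p_M | 1.00 | 5% |

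The row with b = 0.2 is the worst case for that small boost.

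**How much of a crude difference is infection type?** Add an assumed true within-type effect of 0.15 log10. The share due to infection type is d/(d + 0.15). Over p_M of 50%, 70% and 90%, OR 2 or 4, and b from 0.2 to 1.5, it runs from 6% (0.009/0.159) to 75% (0.45/0.60).

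**Does adjustment work?** With infection type as a covariate (2,000 simulations, n = 40, five scenarios), the false-positive rate was 3.7% to 6.1%. The same scenarios unadjusted gave 6% to 48%. This deals with infection type only. It does not make PRNT serotype-specific in a secondary infection, and no illness-day effect was modelled because the documents give nothing to size it.

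**Timing.** If 25% of health-center participants give a second sample, about 100% − 25% = 75% do not. If second-visit serum were used, most health-center participants could not serve as controls, and those who could would have been picked on clinical judgment.

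**The case against.** The strongest reply has four parts.

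- **The antibody boost comes from outside the documents.** This stands: its existence and size are assumptions, so the point is conditional and its size is a range. The other link, between infection type and severity, is the plan's own, as is the absence of stratification or adjustment.
- **Hyperendemicity cuts both ways.** If most mild cases are also secondary, there is little contrast left to confound. This stands too: at 90% secondary in mild cases, OR 2 and a 1.0 log10 boost, the ratio is 1.12 and the false-positive rate 7%. First-visit serum may also carry little boost.
- **No faulty test is written.** Section 6.2 names no severe-versus-mild PRNT test, so the unadjusted test is an inference from the word controls in section 5.6. That is correct, and the defect is an omission. But a control group implies a comparison, and nothing in the plan steers it away from a crude one.
- **The term serotype-specific may mean only titres against each serotype.** That is a fair reading, so this part is mainly a request for clear reporting.

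A reader might also infer that the infecting serotype will be taken from the highest PRNT titre. The documents do not support that: section 5.6 assigns serotype identification to PCR.

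**Conclusion.** The point holds as a risk of confounding, and the plan should deal with it before PRNT specimens are selected. The plan expects infection type to relate to severity and intends to measure it, but uses it in neither the control draw nor the analysis. It also leaves the PRNT visit open although sampling times differ by site and NS1 result.

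The size depends on the assumed shares, boost, SD and group size. With no true effect within infection type and 40 per group, the ratio runs from about 1.1 or less to 4.0, and the unadjusted false-positive rate from about 6% to 86%. The low end applies when nearly all cases are secondary or the boost is small. The direction and size of any illness-day bias are unknown.

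A reader might infer that the contrast would largely re-express primary versus secondary infection. The documents do not support that: they give neither the secondary share nor the boost, and under the assumptions tried infection type explains anywhere from 6% to 75% of a crude difference.

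**What to change.** **Section 5.6.** Name the visit whose serum is used for PRNT, the same for severe and mild cases as far as possible, taking account of who lacks a second sample. Draw the random mild controls within primary/secondary strata using the planned IgM/IgG results, with numbers per stratum set to mirror the severe cases. State which assay and rule define infection type, because the section gives no classification rule.

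**Section 6.2.** Add a PRNT analysis: compare log10 titres against each of DENV-1 to DENV-4 between severe and mild cases, with infection type and illness day at sampling as covariates, or within infection type with illness day as a covariate. Keep the covariates even with a stratified draw, since the draw does not balance illness day. Report PRNT in secondary infections as titre and breadth, not as serotype-specific immunity.

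**Cost.** Protocol wording and a stratified draw from results already planned, with no extra specimens or assays. Illness day follows from fever duration at entry, which the inclusion criterion already requires, and the sampling date. The downside is smaller strata and a narrower serotype-specific claim, since primary infections may be few.

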6.1. Variable

Variables collected include age, gender, demographic characteristics, clinical symptoms, medical history, and history of previous dengue infection. The prevalence, immunologic and virologic characteristics, clinical features, and severity of DENV1-4 infection will also be recorded.

6.2. Statistical analysis

Statistical analysis will include descriptive statistics to summarize the demographic and clinical characteristics of participants. Prevalence estimates of DENV1-4 will be calculated with their respective confidence intervals. Prevalence, demographic and clinical comparisons between DENV-4 and other serotypes will be made using appropriate statistical tests, such as chi-square or Fisher's exact test.

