6.3. Sample size

This study aims to collect data for one year. In accordance to the data reported in 2022, we will collect 100 dengue infection cases from each public health center and 200 cases from the Tangerang District Hospital.

It is expected that the Tangerang District Hospital, Kelapa Dua Public Health Center and Bojong Nangka Public Health Center can represent the population in Tangerang District.

VII. REFERENCES

3. da Costa VG, Marques-Silva AC, Moreli ML. *A meta-analysis of the diagnostic accuracy of two commercial NS1 antigen ELISA tests for early dengue virus detection*. *PLoS One*. 2014 Apr 11;9(4):e94655. doi: 10.1371/journal.pone.0094655. PMID: 24728377; PMCID: PMC3984211.

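### Section 6.2 does not specify any use of primary/secondary infection type when DENV-4 is compared clinically with other serotypes, so a difference in infection mix could pass for, or hide, a serotype effect

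*Combined protocol and SAP*

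**What the plan says.** Section 6.2 plans descriptive statistics, prevalence of each serotype with confidence intervals, and one named between-serotype comparison: "Prevalence, demographic and clinical comparisons between DENV-4 and other serotypes will be made using appropriate statistical tests", with chi-square and Fisher's exact test given as examples. It mentions no stratification, adjustment, interaction or regression, and does not refer to infection type.

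Other parts of the protocol bear on this:

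- Section III hypothesises that "DENV-4 infection is more frequently found at the primary health centers than at the hospital because the clinical symptoms are milder". It also lists infection type next to serotype among the factors expected to matter: "immune status, serotypes, types of infections (primary/secondary) are associated with severity of symptoms".
- Section 2.2 has a matching secondary objective: "To assess human and viral factors associated with severity of febrile illness due to dengue virus infection".
- The background says that secondary "infections of DENV-2, DENV-3, and DENV-4 in Southeast Asia are commonly associated with severe clinical manifestations".
- Section 5.6 (Serology) plans "IgG to determine primary or secondary infection", so the stratifying variable is to be collected.
- Section 6.3 sets the case target: "we will collect 100 dengue infection cases from each public health center and 200 cases from the Tangerang District Hospital".

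**The concern.** By the protocol's own hypothesis, infection type affects the outcome on which DENV-4 is to be compared. A variable that affects the outcome and may be unevenly spread over the comparison groups is a potential confounder. Here it is due to be measured, but the analysis plan makes no stated use of it.

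Two errors are possible. If DENV-4 cases contain more (or fewer) secondary infections than the others, a crude table can show DENV-4 as more severe (or milder) with no serotype effect at all. Conversely, a truly milder DENV-4 with a larger secondary share can look much like the rest. Separately, a pooled result cannot say whether a difference applies to secondary infections, which the background singles out for their health burden. Section 2.2 wants these serotype profiles for vaccine trials and implementation, so a mistaken conclusion about DENV-4 severity would matter.

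The point concerns the clinical and severity comparisons. The prevalence estimates are not affected in this way.

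**Working it through.** **The plan's own figure.** The quotas in section 6.3 give 2 × 100 + 200 = 400 dengue cases. The total is implied, not printed. It is a count target with no stated alpha, power, effect size, feature rate or secondary share, so there is no power calculation to reproduce.

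**Assumed inputs (none is in the documents).** 400 serotyped cases, of which 40, 60 or 100 are DENV-4; a clinical feature present in 15% of primary and 40% of secondary infections unless stated otherwise; infection type classified without error; two-sided 5% tests.

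**Formula.** With s the secondary share in a serotype group, crude risk = s × (risk in secondary) + (1 − s) × (risk in primary). The crude Pearson chi-square was compared with the Mantel-Haenszel test stratified by infection type, over 20,000 simulated studies per setting.

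**(a) No serotype effect, unequal mix.**

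- Shares 85% vs 55%: DENV-4 0.85 × 0.40 + 0.15 × 0.15 = 36.3%; others 0.55 × 0.40 + 0.45 × 0.15 = 28.8%.
- Shares 70% vs 60%: 0.70 × 0.40 + 0.30 × 0.15 = 32.5%; 0.60 × 0.40 + 0.40 × 0.15 = 30.0%.

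**(b) DENV-4 halves the risk in both strata (7.5% vs 15%; 20% vs 40%), shares 90% vs 50%.** Crude risks are 0.90 × 0.20 + 0.10 × 0.075 = 18.8% and 0.50 × 0.40 + 0.50 × 0.15 = 27.5%.

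**(c) DENV-4 milder in primary infection only (5% vs 20%; 40% vs 40% in secondary), share 60% in both groups.** Crude risks are 0.6 × 0.40 + 0.4 × 0.05 = 26% and 0.6 × 0.40 + 0.4 × 0.20 = 32%.

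Share of studies rejecting, for 40 / 60 / 100 DENV-4 cases:

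| Scenario | Crude | Mantel-Haenszel |
|---|---|---|
| (a) 85% vs 55% | about 18 / 22 / 29% | about 5% |
| (a) 70% vs 60% | 7-8% | about 5% |
| (b) 90% vs 50% | about 20 / 28 / 42% | about 67 / 80 / 92% |
| (c) 60% in both | about 11 / 14 / 19% | about 10 / 14 / 20% |

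In (a) the crude rejections are false positives; in (b) they are power. In (c) the stratified summary behaves like the crude test, and only the separate stratum results show where the difference lies.

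**Check with other assumed rates.** Take a severe-disease risk of 5% in primary and 20% in secondary infection, with no serotype effect. Shares of 40% vs 80% give 11.0% vs 17.0% (odds ratio 0.60), and 90% vs 50% give 18.5% vs 12.5% (odds ratio 1.59). The apparent direction depends on the mix alone. With equal shares (70% in both), both tests reject in about 5%.

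**The case against.** Several objections carry weight.

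- **Silence is not pooling.** Section 6.2 introduces its tests as examples and does not rule out stratifying. The supportable statement is that it does not specify any use of infection type. That stands as a gap, because nothing commits the analysis to it.
- **A reader might infer that the documents imply an interaction**, reasoning that DENV-4 can be milder and secondary DENV-4 commonly severe only if the serotype effect depends on infection type. They do not support this. In scenario (b) DENV-4 has half the risk in both strata, yet secondary DENV-4 is still worse than primary (20% vs 7.5%), with the same risk ratio in each. The background names DENV-2, DENV-3 and DENV-4 together and does not rank DENV-4 against the others. An interaction is possible, not implied.
- **The inputs are assumed.** The large effects need strongly unequal mixes; at 70% vs 60% the crude test is near its nominal level. Section 6.3 promises 400 dengue cases, not 400 serotyped ones.
- **Classification will be imperfect.** Section 5.5 takes second specimens from only 25% of health-center participants, chosen by clinical judgment, and section 5.6 gives no IgG rule for secondary infection. If, as an assumption, 30% of secondary infections were labelled primary, the stratified test in (a) at 85% vs 55% would reject in about 9-13%. That is no longer 5%, but still below the crude 18-29%.
- **Infection type is not the only candidate.** Section III also lists age as a severity factor and links DENV-4 to site. Stratifying by infection type alone leaves these uncontrolled. A regression model for the severity objective, with serotype, infection type, their interaction, site and age, could also cover this point, but section 6.2 plans none.

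**Conclusion.** The concern holds as a gap in specification. The clinical comparison of DENV-4 with other serotypes is planned with unstratified two-way tests as the only named examples, while a severity factor that the protocol itself names and plans to measure is not used. If the infection mix differs by serotype, the crude comparison can mislead in either direction. Under the stated assumptions, its false-positive rate runs from 7-8% (70% vs 60%) to 18-29% (85% vs 55%), and its power can fall from 67-92% to about 20-42% (scenario b). If the mix is equal, confounding vanishes, though a difference between strata could remain. The true size is unknown, because the documents give neither shares nor rates. This is a cheap improvement worth making before analysis. It does not show that the planned comparison will be wrong.

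**What to change.** In section 6.2:

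1. Report each DENV-4 versus other-serotype clinical and severity comparison, but not the prevalence estimates, separately for primary and secondary infection, with 95% CIs.
2. Beside the crude result, give a Mantel-Haenszel odds ratio (exact if sparse) as the summary adjusted for infection type.
3. Base any statement about secondary infections on the secondary-stratum estimate. A common odds ratio does not answer that question.
4. State the IgG rule that separates primary from secondary infection, and report cases that cannot be classified as their own category.

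**Cost.** Analysis-plan wording and one more split of tables already planned, with no new assay.

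**Downside.** Strata may be small. If DENV-4 were 5-25% of 400 cases (20-100) and 70% of infections were secondary, both assumed, there would be 0.30 × 20 = 6 to 0.30 × 100 = 30 primary DENV-4 cases. Estimates with intervals therefore suit better than tests alone. Misclassified infection type would leave some residual confounding, which the report should acknowledge.

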5.1. Study design

This study is a prospective observational study that will be conducted in Tangerang Regency, Indonesia. In this study, data will be collected from patients who seek treatment at the Tangerang District Hospital, Kelapa Dua Public Health Center and Bojong Nangka Public Health Center in a one-year period from January 2024 to December 2024. Both public health centers have densely populated areas and have experience in conducting clinical research on COVID-19 vaccination.

Patients suspected of dengue infection will be screened using inclusion and exclusion criteria. Selected participants will be seen at the first visit as clinical data will be collected, routine hematology test and NS-1 RDT will be conducted. Blood specimens will be collected for further testing at Tangerang District Hospital's Infectious Disease Laboratory.

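### The planned comparison of DENV-4 with other serotypes names only unadjusted tests, although patients enter on any fever day up to 7, so features that change over the illness may be confounded by illness day, in either direction

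*Combined protocol and SAP*

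**What the plan says.** - **Analysis.** Section 6.2: "demographic and clinical comparisons between DENV-4 and other serotypes will be made using appropriate statistical tests". The only examples given there are unadjusted ones ("such as chi-square or Fisher's exact test"). No covariate, stratum or model is named.
- **Entry window.** Section 5.2 admits fever or "history of fever with antipyretic use, lasting less than or equal to 7 days". There is no narrower window and no stratum by fever day.
- **First visit.** Section 5.1: "Selected participants will be seen at the first visit as clinical data will be collected, routine hematology test and NS-1 RDT will be conducted". This applies to every participant.
- **Second visit.** Section 5.5 states for inpatients: "The data and specimens to be collected are data at the time of the first visit to the hospital and at the second visit". Their second visit is at discharge if the NS1 rapid test was positive, otherwise 7-14 days after the first. For health centers, "the second data and specimens are only taken as much as 25% of the number of participants of the first visit", at 7-14 days, with participants chosen on clinical judgment.
- **Variables.** Section 6.1: "Variables collected include age, gender, demographic characteristics, clinical symptoms, medical history, and history of previous dengue infection", followed by a sentence that adds severity, among other items. Fever day at assessment is not listed.
- **Hypothesis.** Section III: "DENV-4 infection is more frequently found at the primary health centers than at the hospital", for the stated reason that symptoms are milder. It says nothing about when patients present.

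**The concern.** The first visit is the only time point that covers everyone. At the health centers, 100% − 25% = 75% of participants have no other study visit, so their clinical and blood-count record is a single snapshot on whatever fever day they came. Blood counts, rash and bleeding can differ between the first days of fever and days 4-7. If DENV-4 patients are seen on different fever days from the others, an unadjusted table mixes serotype with timing.

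The plan gives a reason to think this possible: it expects serotype to go with type of site, and the route to a referral hospital may differ in length from the route to a health center. Clinical characteristics by serotype are at the center of the primary and secondary objectives, and Section III expects milder symptoms with DENV-4. For a feature that accumulates over the illness, earlier presentation of DENV-4 would imitate that expectation without any true difference.

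**Working it through.** **The plan's own figures.** Section 6.3 targets 100 + 100 + 200 = 400 dengue cases: 200 from two health centers and 200 from the hospital. The 2022 counts in the background give 2 × (50 to 100) + 200 = 300 to 400, with the hospital figure a minimum. No DENV-4 share, effect size, alpha or power is stated, and there are no data on presentation day by serotype or site. Everything below other than the 200/200 split is therefore an assumption used for illustration.

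**Assumed inputs.** 40 DENV-4 and 360 other cases. A feature is present in 20% of patients seen early (days 0-3) and 60% of those seen late (days 4-7), identically for every serotype. There is no true serotype difference.

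**Formulas.** With E the share seen early, expected frequency = 0.20 E + 0.60 (1 − E) = 0.60 − 0.40 E. With d the absolute difference in frequency, s0 its standard error from the pooled proportion and s1 its unpooled standard error, rejection probability = Φ((d − 1.96 s0)/s1) + Φ((−d − 1.96 s0)/s1).

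**Route A: the day gap arises only through site.** Assume 65% of health-center and 35% of hospital patients are seen early.

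*75% of DENV-4 at health centers.*
- DENV-4 at health centers: 30 of 40. Others: (200 − 30)/360 = 47.2%.
- Early, DENV-4: 0.75 × 0.65 + 0.25 × 0.35 = 57.5%. Early, others: 0.472 × 0.65 + 0.528 × 0.35 = 49.2%.
- Frequency: 37.0% vs 40.3%, a spurious difference of 3.3 points.
- s0 = 0.0816, s1 = 0.0806; rejection = Φ(−1.57) + Φ(−2.40) = 6.6%.

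*90% of DENV-4 at health centers.*
- Others at health centers: (200 − 36)/360 = 45.6%.
- Early: 62.0% vs 48.7%. Frequency: 35.2% vs 40.5%, a spurious difference of 5.3 points.
- s0 = 0.0816, s1 = 0.0798; rejection = Φ(−1.34) + Φ(−2.67) = 9.4%.

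**Route B: a direct serotype gap in timing.** Assume 40% of other cases are seen early (frequency 44%).

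| DENV-4 seen early | DENV-4 frequency | Difference | Rejection |
|---|---|---|---|
| 60% | 36% | 8 points | 15.5% |
| 70% | 32% | 12 points | 29.8% |

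**Can site alone produce Route B?** With 75% of DENV-4 at health centers, the two serotype groups differ by 75 − 47.2 = 27.8 points in health-center share. A 20-point gap in early presentation then needs a site gap of 20/27.8 = 72 points, and a 30-point gap needs 30/27.8 = 108 points, which is impossible. With 90%, the difference in share is 44.4 points and the required site gaps are 45 and 67.5 points.

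**Direction, and whether adjustment works.** A simulation used 400 cases, a DENV-4 share of 5%, 10% or 25%, visit day on 1-7 from a discretized normal (mean 4, SD 1.5, shifted earlier for DENV-4), no true serotype effect, and 2000 runs per scenario. The table shows a shift of 1.24 days.

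| Feature over days 1-7 | DENV-4 vs other | Crude rejection at 5 / 10 / 25% share |
|---|---|---|
| Rising, 10% to 50% | 21.8% vs 30.0% | 9.6 / 17.6 / 37.0% |
| Flat, 30% | 30.0% vs 30.0% | 4.5 / 5.7 / 5.3% |
| Falling, 50% to 10% | 38.2% vs 30.0% | 13.4 / 20.4 / 34.1% |

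With a shift of 0.85 day and a rising feature, crude rejection was 8.5%, 8.9% and 18.8%. With no shift it was about 5%. A Cochran-Mantel-Haenszel test stratified by day stayed at about 4-6% in every scenario.

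**The case against.** **The wording leaves adjustment open.** Chi-square and Fisher's test are given as examples, and Section 6.2 neither restricts the comparison to first-visit data nor names hematology. That is so, and adjustment is not excluded. But the named examples are unadjusted, no stated analysis uses illness day, and an adjustment chosen after seeing the data is not prespecified.

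**Other data exist.** All inpatients and 25% of health-center participants have a second visit, severity is assessed, and interviews and medical records are used, so symptoms need not be a one-day snapshot. This softens the point for symptoms that can be recalled. It does not help blood counts in participants with one visit. A visit 7-14 days later does not standardize the acute-phase record, and the severity assessment has no stated time point or worst-grade rule.

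**The premise is not documented.** This is the strongest objection, and it stands. Section III links DENV-4 to health centers through milder symptoms, not earlier presentation. Milder illness could equally mean later care-seeking, which would reverse the bias. A reader might infer that DENV-4 will look milder as an artefact. The documents do not support that: they give no presentation day by serotype, features that fade would make an earlier-presenting serotype look worse, and flat features give no bias.

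**The size is modest if site is the only route.** This also stands, as Route A shows. A reader might take 16-30% as the expected false-positive rate. That range needs a 20-30 point gap in early presentation between serotypes, for which the documents give no basis.

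**Fever day is not the only confounder.** Section III itself names age and type of infection as severity factors. Adjusting for fever day does not deal with these or with site, which is why results by site are needed as well.

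**Conclusion.** The point holds as a conditional one. The documents establish a 7-day entry window, a first visit that is the only time point covering all participants, and a clinical comparison by serotype for which only unadjusted tests are named. Illness day is therefore uncontrolled. Whether this biases the results depends on two things the documents do not show: that serotypes differ in fever day at presentation, and that the feature compared changes with day. If both hold, the bias may run either way.

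On the assumed inputs, a day gap acting only through site gives about 3 to 5 points and about 7 to 9% rejection against a nominal 5%. The 8 to 12 points and 16 to 30% of Route B apply only with a direct serotype gap in timing. The change is worth making because the remedy is nearly free and held the error rate near nominal in every simulated scenario.

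**What to change.** - **Section 6.1:** add fever day at first visit to the variables.
- **Section 6.2:** add, for example: 'First-visit clinical and hematology variables will be compared between serotypes by regression (logistic for features, linear for counts), or by stratified analysis, with fever day at first visit as a covariate. Crude results will be shown alongside, and results will also be shown by site (hospital, health center).'

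Showing results by site is preferable to relying on site adjustment alone: Section III holds that milder illness is why DENV-4 is seen at health centers, so site may partly reflect the severity being compared.

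The cost is one data field, already needed to apply the first inclusion criterion, and one or a few degrees of freedom in simple models. Design, sample size and patient care are unchanged.
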